8.5.2 Prohibited Medications

The following drugs are not permitted during the course of the study:

- Anticoagulants or antiplatelet agents other than those described above for per-protocol assignment or as rescue or bail-out treatment, by any route (with the exception of parenteral agents used to treat a new clinical event);
- Fibrinolytic agents, unless required to treat a new clinical event, such as acute MI, pulmonary embolism, or stroke, in which case the risks and benefits of such treatment should be considered and, if given, the assigned study drug should be stopped;
- Chronic use (i.e., more than 3 times a week for more than 3 months) of oral or parenteral NSAIDs including both COX-1 and COX-2 inhibitors other than aspirin. Aspirin is permitted in the regimen predefined in the above section on background therapy only. Use of NSAIDs via other routes (e.g., topical, inhaled, intranasal, intraocular, etc.) is not restricted;
- Hormonal contraception;
- Investigational drugs (other than in the study treatment regimen).

Patients on these drugs at the time of enrollment will be excluded from the study.

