All patients will be administered a loading dose of aspirin approximately 325 mg (not exceeding 400mg, if not already on maintenance ASA dose) and will stay on 75-100 mg/day (according to local countries clinical practice guidance) as maintenance therapy. All patients will receive a loading dose of clopidogrel (600 mg) if not already on maintenance dose either before PCI or otherwise at the time of PCI, and then maintain a maintenance dose of 75 mg/day. If the local clinical guidance recommends use of Ticagrelor or Prasugrel, the recommended doses will be: Either before PCI or otherwise at the time of PCI, all patients will receive a loading dose of Ticagrelor 180 mg if not already on a maintenance dose, and then stay on a maintenance dose of 90 mg twice daily. Or either before PCI or otherwise at the time of PCI, all patients will receive a loading dose of Prasugrel 60 mg if not already on a maintenance dose, and then stay on a maintenance dose of 5-10 mg daily.

Patients with symptoms of ACS due to NSTEMI who are being triaged in the Emergency Room/hospital and who are selected for early PCI will be screened for the study. Enrollment should occur be as close to the actual start of PCI as possible. All patients will be given routine care for ACS according to applicable guidelines including analgesics, nitrates, beta-blockers, and potentially additional drugs as needed (anti-arrhythmic drugs, statins, ACE inhibitors/angiotensin II receptor blockers, calcium-channel blockers, proton pump inhibitors, etc).

If a patient meets all the admission criteria and all the eligibility criteria, he/she can be enrolled to receive MT1002 treatment (1 of 3 dose levels) and undergo early PCI (including diagnostic coronary angiography procedure).

Procedure: either radial access/distal radial access PCI or femoral access PCI will be used in this study. It is up to the discretion of the Principal Investigator what type of stent(s), if indicated, will be used.

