7.2 Exclusion Criteria

Individuals meeting any of the following criteria at Screening are ineligible to participate in this study:

1. Cardiogenic shock or prolonged cardiopulmonary resuscitation (CPR).
2. Active bleeding, bleeding diathesis, coagulopathy.
3. Any history of intracranial bleeding or structural abnormalities (intracerebral mass, aneurysm, arteriovenous malformation [AVM]).
4. Prior transient ischemic attack, prior stroke within 6 months.
5. Index MI is STEMI (ST elevation Myocardial Infraction).
6. The following planned procedures within 30 days after enrollment: CABG, valve surgery, or additional invasive procedures.
7. Requirement for oral anticoagulants before Day 7 post IP treatment.
8. Based on investigator's discretion, subject is at high bleeding risk, i.e., CRUSADE (Can Rapid risk stratification of Unstable angina patients Suppress ADverse outcomes with Early implementation of the American College of Cardiology/American Heart Association [ACC/AHA] Guidelines) bleeding risk score >60.
9. Suspected aortic dissection.
10. History of gastrointestinal or genitourinary bleeding within the previous 3 months.
11. Refusal to receive blood transfusion if needed during the study.
12. Major surgery in the last month.
13. History of heparin-induced thrombocytopenia and bleeding diathesis.
14. Severe uncontrolled hypertension, defined as a systolic blood pressure > 180 mmHg and diastolic blood pressure > 100 mmHg up to 24 hours of adequate treatment.
15. Prior (within 30 days prior to enrollment) or planned administration of thrombolytics, glycoprotein IIb/IIIa inhibitors, bivalirudin, or fondaparinux for the index MI. Subcutaneous injections of unfractionated heparin and low molecular weight heparin are allowed up to 4 hours and 8 hours, respectively, before study drug. Use of intravenous unfractionated heparin may be continued up until the time of enrollment (just prior to PCI), if ACT is < 200 seconds.
16. Known relevant hematological deviations: hemoglobin (male) < 11 g/dL hemoglobin (female) < 10 g/dL, hematocrit < 35%, platelet count < 100,000 cells/ μ L.
17. Use of Coumadin derivatives and/or Factor Xa inhibitor drugs within the last 7 days.

18. Chronic therapy with non-steroidal anti-inflammatory drugs (NSAIDs; except aspirin) (NSAID use is defined as chronic if these medications are taken more than three times a week for more than three months), cyclooxygenase (COX)-2 inhibitors within 1 month before screening.

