8.2 Dosage Schedule

Patients will receive MT1002 IV followed by MT1002 infusion for 4 hours. This regimen was found safe and well tolerated in Phase 1. MT1002 will be initiated as close to the start of PCI as possible. MT1002 should be initiated during diagnostics angiography when indication for PCI is confirmed, provided the early PCI is indicated right after the coronary angiography. PCI can start after MT1002 initiation as soon as ACT is confirmed to be ≥ 200 sec or within 30 min after MT1002 starts, whichever occurs first. MT1002 will be administered by an intravenous injection of 0.90 mg/kg, 1.2 mg/kg, 0.75 mg/kg or 0.6 mg/kg (depending on the dose selected for the cohort) via IV access prior to the PCI procedure, immediately followed by an IV infusion of 1.8 mg/kg/hour, 2.3 mg/kg/hour, 1.6 mg/kg/hour or 1.2 mg/kg/hour (depending on the dose selected for the cohort) until completion of the procedure.

Patients will be discharged from the hospital when they are stable, as defined by the Investigator's judgment. Patients will be followed for 30 days from study drug dosing.

Three doses of MT1002 will be evaluated in this study as noted in the table below. The first dose level is 0.90 mg/kg initial loading dose (bolus intravenous injection) + 1.8 mg/kg/h (infusion) for 4 hours. The second dose level will be based on the results from the first cohort (If the dose is escalated, then the second dose level is 1.2 mg/kg initial loading dose (bolus intravenous injection) + 2.3 mg/kg/h (infusion) for 4 hours; if the dose is de-escalated, then the second dose level is 0.6 mg/kg initial loading dose (bolus intravenous injection) + 1.2 mg/kg/h (infusion) for 4 hours). The third dose will be based on the results from the initial 2 cohorts (Table 3). The goal is to achieve a target ACT of 200 to 300 sec (within 30 minutes after infusion initiation) during the continuous infusion period of MT1002.

Patients who are enrolled but do not undergo PCI (e.g., because of PCI contraindication revealed after coronary angiography or due to exclusion criteria) will be replaced for the study. However, the patients will be evaluated as safety population.

Dose adjustment guideline for cohort 3 dosing regimen is below. All adjustment will be documented in the patient's source document in detail:

- Bolus and maintenance dosing

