The Investigator is responsible for ensuring that procedures and expertise are available to handle medical emergencies that may occur during the study.

Medications taken by or administered to the patient for the time period before Screening will be recorded in the eCRF. After the baseline visit, medication to treat minor treatment-emergent illness(es) is generally permitted.

Any medication or therapy that is taken by or administered to the patient during the course of the study must be recorded in the eCRF. The entry must include the dose, regimen, route, indication, and dates of use.

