9 STUDY PROCEDURES

Table 4 outlines the timing of procedures and assessments to be performed throughout the study. Section 11.5 specifies laboratory assessment samples to be obtained. See Sections 100 and 111 for additional details regarding efficacy/pharmacodynamic assessments and safety assessments, respectively.

Table 4 Schedule of Assessments

Assessment	Screening	Day of Procedure, Day 1			Follow-up		
Study Day	On admission	Pre PCI (Baseline)	During PCI ^a (≤ 72 hours from admission depending on the risk criteria)	Post PCI	Day 2 ^b	Day 14±1	End of Study Day 30±2
Informed consent	X						
Inclusion/exclusion criteria	X	X					
Significant medical and surgical history	X						
Demographics	X						
Cardiac and noncardiac medication on	X						
Physical examination ^c	X			X	X	X	X
Weight, height, body mass index	X						
Vital signs		X ^l	X	X	X	X	X
12-lead electrocardiogram		X ^l		X	X	X	X
CK-MB, cardiac troponin I (or troponin T) ^d		X ^l X	X	X	X	X	X
ACT, aPTT, PT, TT, FIB, INR		X ^l	X ^k	X	X	X	X
PA (by PFA100 or PFA200) ^e		X ^l	X	X	X	X	X
Hematocrit, hemoglobin, platelet count, RBC and WBC counts		X ^l	X	X	X	X	X
Serum chemistry including lipid panel and HbA1c ^f	X				X	X	X
Serum or urine pregnancy test (women of childbearing potential only)	X						X
Percutaneous coronary intervention			X				
Aspirin ^g	X	(X)			◀-----▶		
Clopidogrel (or Ticagrelor or Prasugrel) ^h	X	(X)			◀-----▶		
Enrollment to MT1002		X					
Administration of MT1002 ⁱ		X	X	X			
TIMI flow grade		X	X				
Pharmacokinetic blood sampling ^j		X	X	X	X		
Concomitant medication review	X	X	X	X	X	X	X
Bleeding adverse events (BARC)		X	X	X	X	X	X
Other adverse events	X						

Assessment	Screening	Day of Procedure, Day 1			Follow-up		
Study Day	On admission	Pre PCI (Baseline)	During PCI ^a (≤ 72 hours from admission depending on the risk criteria)	Post PCI	Day 2 ^b	Day 14±1	End of Study Day 30±2
Discharge					X		
Study close out							X

Abbreviations: ACT, activated clotting time; aPTT, activated partial thromboplastin time; BARC, Bleeding

Academic Research Consortium; CK, creatine kinase; HbA1c, glycosylated hemoglobin; min, minutes; PA, platelet aggregation; PCI, percutaneous coronary intervention; PT, prothrombin time; RBC, red blood cell; sec, seconds; TIMI, thrombolysis in myocardial infarction; WBC, white blood cell.

- ^a PCI should start after MT1002 initiation as soon as ACT is confirmed to be ≥ 200 sec or within 30 min after MT1002 start, whichever occurs first.

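### Section 8.5.2 limits systemic NSAIDs on study only by a three-month chronic-use test, which by elapsed time no course started after enrollment can meet before the last visit

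*Combined protocol and SAP*

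**What the plan says.** Section 8.5.2 (Prohibited Medications) sets out what patients may not take during the study. Its NSAID item reads "Chronic use (i.e., more than 3 times a week for more than 3 months) of oral or parenteral NSAIDs" and covers both COX-1 and COX-2 inhibitors other than aspirin. The same item allows aspirin only in the predefined background regimen and leaves non-systemic routes unrestricted. The section closes with "Patients on these drugs at the time of enrollment will be excluded from the study".

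Exclusion 18 in section 7.2 uses the same test at entry: "NSAID use is defined as chronic if these medications are taken more than three times a week for more than three months".

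Follow-up is short. Section 8.2 states "Patients will be followed for 30 days from study drug dosing", and the last column of Table 4 in section 9 is "End of Study Day 30±2".

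Elsewhere the plan is permissive or general. Section 6.1 provides "routine care for ACS according to applicable guidelines including analgesics", and section 8.5.1 says that after baseline "medication to treat minor treatment-emergent illness(es) is generally permitted". Neither sets a limit on NSAIDs.

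**The concern.** A three-month definition makes sense when an investigator looks back over a patient's history. Used going forward in a study of about a month, it has almost nothing to act on. The item seems meant as a real limit, because it contrasts systemic routes with routes that are free of restriction, and it holds aspirin to a fixed regimen. Yet as written, aspirin outside that regimen is a breach, while another systemic NSAID taken every day to the last visit need not be.

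What is at stake is mainly safety. Every patient is to take aspirin plus a P2Y12 inhibitor through Day 30, and section 8.5.1 strongly recommends proton pump inhibitors because of gastrointestinal bleeding. A lesser matter is the bleeding count. Section 5.2.1 gives no time window for the BARC 3–5 co-primary endpoint, and BARC bleeding is assessed at Day 14 and Day 30 (section 9.2.6). In Phase 1 healthy volunteers, clotting and platelet values were close to baseline by Day 2 (section 4.2.2). A later bleed associated with an NSAID would still be counted.

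**Working it through.** The plan states no figure to reproduce. The check compares two durations.

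**Inputs**
- Threshold: more than 3 months (sections 8.5.2 and 7.2).
- Last visit: Day 30±2, so Day 28 to Day 32 (Table 4, section 9.2.6).
- Month convention: not stated, so a range is used. Three 4-week months are 84 days. Three calendar months are 89 to 92 days.
- Time before PCI, for sensitivity only: 96 hours, which inclusion 3 gives as an ideal and not a hard limit.

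**Longest course started on study**
- From Day 1 to the latest last visit, counted inclusively: 30 + 2 = 32 days.

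**Days needed to exceed three months**
- Shortest convention: 84 + 1 = 85 days. Longest: 92 + 1 = 93 days.

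**Comparison by elapsed time**
- 32/85 = 38% and 32/93 = 34%. The course reaches about a third of the threshold on any convention.
- Counting from presentation 96 hours before PCI: 32 + 4 = 36 days, still 84 − 36 = 48 to 92 − 36 = 56 days short of three months.

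**Comparison by planned duration**
- An open-ended prescription started on study could be classed as exceeding three months and so be barred.
- A course planned to end by the last visit has a planned length of at most 32 days and is allowed.

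**Where the item does work**
- At enrollment, it screens out patients already on chronic NSAIDs, together with exclusion 18.
- On study, it can catch a patient who brings in prior use and continues. The prior use needed is 85 − 32 = 53 days at the least and 93 − 28 = 65 days at the most.

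**Whether another rule closes the gap**
- The first item of section 8.5.2 bars other antiplatelet agents. NSAIDs have their own, narrower item, and reading them into the first would make that item redundant.
- The statements on routine analgesics (section 6.1) and on minor illness (section 8.5.1) set no NSAID limit.

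**The case against.** The strongest reply has four parts.

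- **Reading of the term.** Chronic use may be meant by intended duration. This stands in part. A reader might infer that no NSAID course started on study could ever be barred, and the text does not support that, because an open-ended prescription could fall under the rule. Courses planned to end by the last visit escape on both readings.
- **Existing controls.** Care follows guidelines and local practice. Section 8.5.1 requires dose, regimen, route, indication and dates for every medication. Section 11.6.1 requires an onset date and a causality rating for each adverse event, and Table 8 weighs other therapies. A late bleed associated with an NSAID could therefore be recognized, so the benefit to the bleeding count is small. These controls record and interpret NSAID use. They do not make it a protocol deviation.
- **No measured effect.** A reader might infer a biased bleeding rate or a distorted dose decision. The documents give no NSAID usage rate and the analysis is descriptive, so neither can be supported.
- **The borrowed frequency.** Nothing in the documents justifies 3 times a week as a safety limit, and it would still allow a dose on Day 1 while MT1002 is active. This stands, and it is why any stricter limit belongs to the clinical team.

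A further tempting reading is that COX-2 use in the month before screening excludes a patient while daily COX-2 use afterwards is allowed. That depends on whether the phrase "cyclooxygenase (COX)-2 inhibitors within 1 month before screening" in exclusion 18 is a separate bar or is governed by the opening words on chronic therapy. The punctuation does not settle it, so nothing here relies on it.

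**Conclusion.** The point holds in a limited form. The on-study NSAID rule cannot be breached, by elapsed time, by any course started after enrollment: 32 days at most against at least 85. By planned duration, it reaches only courses intended to run beyond three months. Near-daily systemic NSAID use alongside dual antiplatelet therapy can therefore comply with the protocol for the whole of follow-up.

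This rests on counting from Day 1 to Day 32 and on there being no other on-study NSAID limit in the document. It does not depend on which month convention is used. The rule keeps its function at entry and for patients who bring in about two months of use. The gap does not threaten the validity of the trial. It is a safety rule that does not do its stated job and is cheap to repair.

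**What to change.** Make two edits in section 8.5.2.

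1. Reword the NSAID item to: *Oral or parenteral NSAIDs, including COX-1 and COX-2 inhibitors other than aspirin, more than 3 times a week from enrollment through the End of Study visit (Day 30±2).* The sentences on aspirin and on other routes stay. Any stricter limit, for example during the infusion, is for the clinical team to set.
2. Keep the closing sentence, "Patients on these drugs at the time of enrollment will be excluded from the study", and add: *except that NSAID and COX-2 inhibitor use before enrollment is judged by exclusion criterion 18.* Without this, the new limit would become a wider entry exclusion.

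Exclusion 18 stays as it is. A patient who enters on NSAID use that it allows would cut back to the new limit from enrollment.

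The cost is a small restriction on analgesic choice and a protocol amendment. Because the change bears on patient safety, it may not qualify as administrative under section 15.7.1 and may need regulatory and ethics approval at about 13 planned sites in four countries. Cohort 1's six patients had already been treated when version 6.0 was written, so at most 18 − 6 = 12 of the planned maximum could benefit. Including it in the next amendment is reasonable. It needs no new data, visit or analysis.

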9 STUDY PROCEDURES

Table 4 outlines the timing of procedures and assessments to be performed throughout the study. Section 11.5 specifies laboratory assessment samples to be obtained. See Sections 100 and 111 for additional details regarding efficacy/pharmacodynamic assessments and safety assessments, respectively.

Table 4 Schedule of Assessments

Assessment	Screening	Day of Procedure, Day 1			Follow-up		
Study Day	On admission	Pre PCI (Baseline)	During PCI ^a (≤ 72 hours from admission depending on the risk criteria)	Post PCI	Day 2 ^b	Day 14±1	End of Study Day 30±2
Informed consent	X						
Inclusion/exclusion criteria	X	X					
Significant medical and surgical history	X						
Demographics	X						
Cardiac and noncardiac medication on	X						
Physical examination ^c	X			X	X	X	X
Weight, height, body mass index	X						
Vital signs		X ^l	X	X	X	X	X
12-lead electrocardiogram		X ^l		X	X	X	X
CK-MB, cardiac troponin I (or troponin T) ^d		X ^l X	X	X	X	X	X
ACT, aPTT, PT, TT, FIB, INR		X ^l	X ^k	X	X	X	X
PA (by PFA100 or PFA200) ^e		X ^l	X	X	X	X	X
Hematocrit, hemoglobin, platelet count, RBC and WBC counts		X ^l	X	X	X	X	X
Serum chemistry including lipid panel and HbA1c ^f	X				X	X	X
Serum or urine pregnancy test (women of childbearing potential only)	X						X
Percutaneous coronary intervention			X				
Aspirin ^g	X	(X)			◀-----▶		
Clopidogrel (or Ticagrelor or Prasugrel) ^h	X	(X)			◀-----▶		
Enrollment to MT1002		X					
Administration of MT1002 ⁱ		X	X	X			
TIMI flow grade		X	X				
Pharmacokinetic blood sampling ^j		X	X	X	X		
Concomitant medication review	X	X	X	X	X	X	X
Bleeding adverse events (BARC)		X	X	X	X	X	X
Other adverse events	X						

Assessment	Screening	Day of Procedure, Day 1			Follow-up		
Study Day	On admission	Pre PCI (Baseline)	During PCI ^a (≤ 72 hours from admission depending on the risk criteria)	Post PCI	Day 2 ^b	Day 14±1	End of Study Day 30±2
Discharge					X		
Study close out							X

Abbreviations: ACT, activated clotting time; aPTT, activated partial thromboplastin time; BARC, Bleeding

Academic Research Consortium; CK, creatine kinase; HbA1c, glycosylated hemoglobin; min, minutes; PA, platelet aggregation; PCI, percutaneous coronary intervention; PT, prothrombin time; RBC, red blood cell; sec, seconds; TIMI, thrombolysis in myocardial infarction; WBC, white blood cell.

- ^a PCI should start after MT1002 initiation as soon as ACT is confirmed to be ≥ 200 sec or within 30 min after MT1002 start, whichever occurs first.
- ^b Day 2 lasts until 24 hours ± 1 hour after the MT1002 intravenous injection start on Day 1 and until study-related procedures are complete. Patients will be discharged from the hospital when they are stable according to local standard of care.
- ^c Physical examination is to be performed on Admission Day 1 and includes general appearance, head, eyes, ears, nose, and throat; and cardiovascular, respiratory, gastrointestinal, dermatological, neurological, musculoskeletal, lymphatic, and other systems at the discretion of the Investigator. Brief physical examination should be performed on all other visits from Post-PCI Day 1 onwards and includes general appearance, cardiovascular, respiratory, gastrointestinal, and other at the discretion of the Investigator.
- ^d CK-MB, cardiac troponin I (troponin T can be measured if the local site does not have the troponin I test) to be collected at Screening; immediately before PCI (Day 1 predose); and 0.5 (± 5 mins), 4 (-5 to 10 mins, 5-10 min before the infusion completion), 6 (± 15 mins), 8 (± 15 mins), and 24 (± 15 mins) hours post dose initiation.
- ^e The PA (by PFA100 or PFA200) test should be conducted within 15 min of sample collection. Platelet aggregation sampling to be done at Screening; at 5 (± 1) min after MT1002 intravenous injection; and 0.5 (± 5 mins), 4 (-5 to 10 mins, 5-10 min before the infusion completion), 6 (± 15 mins), 8 (± 15 mins), and 24 (± 15 mins) hours post dose initiation.
- ^f Lipid panel only assessed at Screening and Day 30; HbA1c assessed at Screening only. For the other chemistry parameters, see Section 11.5.
- ^g Aspirin approximately 325 mg (not exceeding 400mg) loading dose on admission, followed by 75-100 mg/day (according to local countries clinical practice guidance). No loading dose if patient is already on chronic treatment with aspirin.
- ^h Clopidogrel 600 mg loading dose on admission, followed by 75 mg/day. If the local clinical guidance recommends use of Ticagrelor or Prasugrel, the recommended doses will be: Ticagrelor 180 mg loading dose on admission, followed by a maintenance dose of 90 mg twice daily. Or Prasugrel 60 mg loading dose on admission, followed by a maintenance dose of 5-10 mg daily. No loading dose if patient is already on chronic treatment with clopidogrel or Ticagrelor or Prasugrel.
- ⁱ MT1002 will be initiated as close to the start of PCI as possible. MT1002 should be initiated during diagnostics angiography when indication for PCI is confirmed, provided the early PCI is indicated right after the coronary angiography. PCI can start after MT1002 initiation as soon as ACT is confirmed to be ≥ 200 sec or within 30 min after start of MT1002, whichever occurs first.
- ^j Pharmacokinetic samples will be taken at Day 1 pre-dose; at 5 (± 1) min after MT1002 intravenous injection; and 0.5 (± 5 min), 4 (-5 to 10 mins, 5-10 min before the infusion completion), 6 (± 15 min), 8 (± 15 min), and 24 (± 15 min) hours post-dose initiation.

- ^k ACT, aPTT, and PT, TT, FIB, INR will be taken at Screening; on Day 1 pre-dose; at 5 (± 1) min after MT1002 intravenous injection; and 0.5 (± 5 min), 4 (-5 to 10 mins, 5-10 min before the infusion completion), 6 (± 5 min), 8 (± 15 min), and 24 (± 15 min) hours post-dose initiation.
- l Between screening and Pre-PCI within 48 hours, Vital signs, 12-lead ECG, CK-MB, cardiac troponin I (troponin T can be measured if the local site does not have the troponin I test), ACT, aPTT, PT, TT, FIB, INR, PA (PFA100 or PFA 200), Hematocrit, hemoglobin, platelet count, RBC and WBC counts take once; screening and Pre-PCI beyond 48 hours, should take twice before PCI.

Table 5 Time Points for Platelet Aggregation, Cardiac Biomarkers, Coagulogram, and Pharmacokinetics

Time points/ blood tests	Screening	Day1 pre-dose	5 min (± 1 min) post-dose initiation	0.5 h (± 5 min) post-dose initiation	4h (-5 to 10 min) post-dose initiation, 5-10 min before the infusion completion)	6h (± 15 min) post-dose initiation	8 h (± 15 min) post-dose initiation	24 h (± 15 min) post-dose initiation
PA	X		X	X	X	X	X	X
Cardiac biomarkers ^a	X	X		X	X	X	X	X
ACT, aPTT, PT, TT, FIB, INR	X	X	X	X	X	X	X	X
PK		X	X	X	X	X	X	X

Abbreviations: ACT, activated clotting time; aPTT, activated partial thromboplastin time; h, hours; PA, platelet aggregation; min, minutes; PK, pharmacokinetics; PT, prothrombin time; TT, Thrombin time; FIB, Fibrinogen; INR, International Normalized Ratio.

^a Creatine kinase-MB, cardiac troponin I (troponin T can be measured if the local site does not have the troponin I test).

